7.1. Study and Study Drug Stopping Criteria

7.1.1. Study Stopping Criteria

Blinded safety review including, but not limited to, laboratory values, vital signs, ECGs, and AEs will be conducted regularly throughout the study and will assess whether any of the following criteria are met:

- One patient experiences a Grade V CTCAE considered related to study medication by the Investigator, or
- Two patients experience the same Grade IV CTCAE considered related to study medication by the Investigator, or
- Three patients experience the same Grade III CTCAE considered related to study medication by the Investigator

Note: Causality of AEs will be determined by the Investigator based on the 4-category system specified in Appendix 6.

In the event that study enrollment and/or dosing is stopped due to one or more of the criteria specified above, the causality of these adverse events will be further investigated by an Independent Medical Monitor (IMM); if adverse events are deemed to be unrelated to study drug (i.e., TERN-501, TERN-101, or TERN-501+TERN-101) by the IMM, then enrollment and/or dosing may resume.

The Sponsor may temporarily or permanently stop the study at any time for safety concerns.

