Assessment of Intensity

The Investigator will be asked to provide an assessment of the severity of the AE using NCI CTCAE v5.0 categories as follows:

- Grade 1: Mild; asymptomatic or mild symptoms; clinical or diagnostic observations only; intervention not indicated.
- Grade 2: Moderate; minimal, local, or noninvasive intervention indicated; limiting age appropriate instrumental ADL.
- Grade 3: Severe or medically significant but not immediately life-threatening; hospitalization or prolongation of hospitalization indicated; disabling; limiting self-care ADL.
- Grade 4: Life-threatening consequences; urgent intervention indicated.
- Grade 5: Death related to AE.

For detailed organ system AE severity grading, please refer to NCI CTCAE v5.0: https://ctep.cancer.gov/protocoldevelopment/electronic applications/docs/CTCAE v5 Quick Reference 8.5x11.pdf

Assessment of Causality

- The Investigator is obligated to assess the relationship between study drug and each occurrence of each AE and/or SAE.
- The Investigator (or designee) will make a determination of the relationship of the AE to the study drug using a 4-category system according to the following guidelines:
 - Not Related: The AE is definitely caused by the subject's clinical state or the study procedure/conditions.
 - **Unlikely Related:** The temporal association between the AE and the drug is such that the drug is not likely to have any reasonable association with the AE.
 - Possibly Related: The AE follows a reasonable temporal sequence from the time of drug administration but could have been produced by the subject's clinical state or the study procedures/conditions.
 - Related: The AE follows a reasonable temporal sequence from administration of the drug, abates upon discontinuation of the drug, follows a known or hypothesized cause effect relationship, and (if appropriate) reappears when the drug is reintroduced.
- For each AE and/or SAE, the Investigator **must** document in the medical notes that he/she has reviewed the AE and/or SAE and has provided an assessment of causality.
- There may be situations in which an SAE has occurred and the Investigator has minimal information to
 include in the initial report to the Sponsor or designee. However, it is very important that the Investigator
 always make an assessment of causality for every event before the initial transmission of the SAE data to
 the Sponsor or designee.

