8.2.2. Patient Incidence of Adverse Events

6.2.2. I dient incluence of Adverse Events

Summaries will be displayed by SOC and PT and will be ordered by descending order of group 7 incidence of system organ class and preferred term within each system organ class. Summaries of the following types will be presented:

- Patient incidence of TEAEs by MedDRA SOC and PT.
- Patient incidence of TEAEs leading to study drug discontinuation by MedDRA SOC and PT. This is a subset of the AEs where Action Taken with Study Drug is checked as "Drug Withdrawn."
- Patient incidence of TEAEs leading to study drug interruption by MedDRA SOC and PT. This is a subset of the AEs where Action Taken with Study Drug is checked as "Drug Interrupted."
- Patient incidence of TEAEs leading to study discontinuation by MedDRA SOC and PT (subset of the AEs where Reason for Discontinuation on the End of Study CRF is "Adverse Event").
- Patient incidence of TEAE leading to death by MedDRA SOC and PT.
- Patient incidence of TEAEs by MedDRA SOC, PT, and highest severity (CTCAE grade). At each level of patient summarization, a patient is classified according to the highest severity if the patient reported 1 or more events. AEs with missing severity (CTCAE grade) will be considered Grade 3 (severe) for this summary.
- Patient incidence of CTCAE Grade 3 or higher TEAEs by MedDRA SOC and PT. At each level of patient summarization, a patient is classified according to the highest severity if the patient reported 1 or more events. AEs with missing severity (CTCAE grade) will be considered Grade 3 (severe) for this summary.
- Patient incidence of treatment-related TEAEs by MedDRA SOC and PT. Related AEs
 are those with relationships reported as "Related" or "Possibly Related". At each level
 of patient summarization, a patient is classified according to the closest relationship to
 study drug if the patient reported 1 or more events. AEs with a missing relationship
 will be considered related for this summary.
- Patient incidence of treatment-related CTCAE Grade 3 or higher TEAEs by MedDRA SOC and PT. At each level of patient summarization, a patient is classified according

CONFIDENTIAL

to the highest severity if the patient reported 1 or more events. AEs with missing severity (CTCAE grade) will be considered Grade 3 (severe) for this summary. AEs with a missing relationship will be considered related for this summary.

• Patient incidence of serious TEAEs by MedDRA SOC and PT.

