The following listings will be presented by treatment group and patient, include study day event started and the duration of event:

- All adverse events.
- Serious adverse events (subset of the AEs where serious is marked as "Yes").
- Adverse events leading to study drug interruption (subset of the AEs where Action Taken with Study Drug is checked as "Study drug interrupted").
- Adverse events leading to study drug discontinuation (subset of the AEs where Action Taken with Study Drug is checked as "Study drug discontinued").
- Adverse events leading to study discontinuation (subset of the AEs where Reason for Discontinuation on the End of Study CRF is "Adverse Event").
- CTCAE Grade 3 or higher adverse events (subset of AEs where severity is marked as CTCAE Grade 3, 4, or 5).
- Related adverse events (subset of the AEs where relationship marked as "Definitely Related" or "Possibly Related").
- CTCAE Grade 3 or higher treatment-related adverse events (subset of AEs where severity is marked as CTCAE Grade 3, 4, or 5).

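### As written, the SAP's related-AE listing omits every event rated Related; the Grade 3+ related listing, the Action Taken labels and the hemoglobin unit also need correction

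*SAP*

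**What the plan says.** **Causality.** Protocol Appendix 6 (Assessment of Causality) has the investigator rate each event "using a 4-category system according to the following guidelines": Not Related, Unlikely Related, Possibly Related and Related. The top category is Related, defined as "The AE follows a reasonable temporal sequence from administration of the drug, abates upon discontinuation of the drug" together with further conditions. Protocol 7.1.1 points to the same scale: "Causality of AEs will be determined by the Investigator based on the 4-category system specified in Appendix 6".

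In the SAP 8.2.2 tables, related AEs "are those with relationships reported as 'Related' or 'Possibly Related", and a missing relationship counts as related for those summaries. In the listings of the same section the rule is "Related adverse events (subset of the AEs where relationship marked as 'Definitely Related' or 'Possibly Related".

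**Grade 3+ treatment-related listing.** SAP 8.2.2 defines it as "CTCAE Grade 3 or higher treatment-related adverse events (subset of AEs where severity is marked as CTCAE Grade 3, 4, or 5". No relationship condition is stated.

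**Action taken.** For discontinuation, the table takes AEs where "Action Taken with Study Drug is checked as 'Drug Withdrawn", and the listing takes AEs where "Action Taken with Study Drug is checked as 'Study drug discontinued". For interruption, the table uses *Drug Interrupted* and the listing uses *Study drug interrupted*.

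**Hemoglobin.** SAP 8.3 asks for the number and percentage of patients with Hg below 10 mg/dL, next to a hematocrit cut-off of 30%. It also says that laboratory parameters are summarized in conventional units.

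**The concern.** These are operative selection rules in a final SAP (Version 2.0), and a programmer can apply them exactly as printed. A reader uses the dedicated listings to go through attributed, severe and treatment-stopping cases one by one, and expects them to reconcile with the incidence tables. Under the printed rules, the listing titled as related would lack the events with the strongest attribution. The listing titled as Grade 3+ treatment-related would contain events judged unrelated. A table or listing of discontinuations or interruptions could come out short or empty. The low-hemoglobin count could be zero whatever the data showed. Getting the right outputs would then depend on a programmer noticing the slips and departing from the SAP without a record.

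**Working it through.** The SAP states no derived figure to reproduce here. The check compares the labels as sets and converts one unit.

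**1. Causality filters against the protocol scale**

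| Protocol category (Appendix 6) | SAP 8.2.2 table | SAP 8.2.2 listing |
|---|---|---|
| Not Related | no | no |
| Unlikely Related | no | no |
| Possibly Related | yes | yes |
| Related | yes | **no** |
| *Definitely Related* (not on the scale) | not used | named, matches nothing |

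The table selects 2 of 4 categories and the listing selects 1 of 4. The difference is exactly the Related category. With Related put in place of Definitely Related, both select the same 2 of 4.

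**2. The two Grade 3+ listings.** The general Grade 3+ listing, two bullets above the treatment-related one, has the same stated subset: severity of CTCAE Grade 3, 4 or 5. Identical conditions return identical records. As written, the treatment-related listing is therefore the general listing under another title, and it includes any Grade 3 to 5 event rated Not Related or Unlikely Related.

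**3. Action Taken.** Each pair gives two different values for one CRF field (*Drug Withdrawn* against *Study drug discontinued*; *Drug Interrupted* against *Study drug interrupted*). A single response option has one wording, so at most one member of each pair can match the CRF verbatim. SAP Section 1 cites the eCRF, version 1.00, as a source, but neither document reproduces its code list. The check stops there.

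**4. Hemoglobin unit.**
- Printed cut-off: 10 mg/dL ÷ 1,000 = 0.01 g/dL.
- Cut-off in g/dL: 10 g/dL × 1,000 = 10,000 mg/dL, which is 1,000 times the printed value.
- Illustrative values of 5, 7, 10, 12 and 17 g/dL equal 5,000 to 17,000 mg/dL. None is below 10 mg/dL, so the count is zero if the printed unit is applied.
- If a program compares results held in g/dL with the bare number 10, values of 5 and 7 are flagged and 10, 12 and 17 are not. The count is then the intended one.
- Plausibility against the adjacent hematocrit criterion: hemoglobin = hematocrit × mean corpuscular hemoglobin concentration (MCHC). The documents give no MCHC, so I assume 30 to 36 g/dL. Then 0.30 × 30 = 9.0 g/dL and 0.30 × 36 = 10.8 g/dL. A cut-off of 10 g/dL falls inside that range, which supports g/dL as the intended unit.

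**The case against.** The strongest reply is that these are drafting slips with little reach. Much of that stands, and it rules out several stronger readings.

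- *A reader might infer that the secondary safety endpoint is compromised.* It is not. That endpoint is patient incidence of TEAEs (SAP 2.2.2.1), and its table uses no causality or action filter. The treatment-related incidence table uses the correct labels.
- *A reader might infer that strongly attributed events are hidden.* They are missing only from the dedicated listing. The all-AE listing has no causality filter and shows every one, and the serious and Grade 3+ listings show those that qualify. The study stopping criteria and study drug discontinuation rules (Protocol 7.1.1 and 7.1.2) rest on the investigator's judgment during the study, not on these listings.
- *A reader might infer that the hemoglobin count is always zero.* That holds only if the printed unit is applied. Low values would also show in the hematocrit count, the descriptive statistics, the CTCAE grading (SAP 8.3.1) and the shift tables (SAP 8.3.5).
- *A reader might infer that the action labels are shown to be wrong against the CRF.* The documents show only that the SAP disagrees with itself. An output would be empty only under verbatim matching, and the paired wordings are plainly meant as the same response.
- *A reader might infer that the rule counting a missing relationship as related must carry over to the listings.* SAP 8.2.2 limits that rule to the summaries.

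It can also be said that the title of the Grade 3+ treatment-related listing implies a relatedness condition, and that the shells mentioned in SAP 3.1 may already state it. That may be so, but the shells are not available here. The bullet just above, which would supply the definition of related, carries the wrong label. The mismatches in the SAP text therefore remain.

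**Conclusion.** The point holds as a set of wrong or inconsistent selection rules with limited reach.

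- **Related-AE listing:** it selects one protocol category instead of two, so all events rated Related are omitted. How many events that is cannot be stated from the documents.
- **Grade 3+ treatment-related listing:** its stated condition is identical to that of the general Grade 3+ listing, so unrelated events are included.
- **Hemoglobin:** the unit is wrong by a factor of 1,000. The count is zero if the unit is applied as printed, and correct if 10 is compared with g/dL values.
- **Action Taken:** the SAP is internally inconsistent. Which wording is right cannot be settled without the eCRF.

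This assumes that the eCRF carries the protocol's four causality labels, that the filters are programmed as written, that Hg means hemoglobin and that hemoglobin is reported in g/dL. If the eCRF used other causality labels, the table and the listing would still disagree with each other. The listings and one laboratory count should be corrected; no efficacy or safety endpoint is put in doubt.

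**What to change.** 1. In the SAP 8.2.2 listings, define related AEs as Related or Possibly Related, as the tables do.
2. Add that relatedness condition to the Grade 3+ treatment-related listing, alongside the severity condition.
3. Take the Action Taken values from the eCRF code list and use that one set in both tables and listings.
4. In SAP 8.3, change the criterion to Hemoglobin < 10 g/dL.
5. Optionally, state whether AEs with a missing relationship appear in the related listings, so that listings and tables reconcile.

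The cost is SAP wording and the matching programming and shell specifications. No new data, design change or clinical rule is involved.

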8.2.3. Pruritus

For patients who report AEs consistent with pruritus at the visit, a qualified staff member will administer the Pruritus Numerical Rating Scale (see Appendix 8 of the study protocol). The Pruritus Numerical Rating Scale assesses a patient's severity of itching on average and at its worst point, in the past 24 hours, on a scale of 0 (no itching) to 10 (worst imaginable itch). Pruritus events will be identified in the ADAE.

Treatment-emergent pruritus is defined as any preferred term including "Prur".

CONFIDENTIAL

A separate by-patient listing for pruritus events will be provided with associated Pruritus Numerical Rating Scale results, if applicable.

8.3. Clinical Safety Laboratory Evaluations

All laboratory assessments are specified in Appendix 1 of the study protocol. Laboratory parameters will be summarized in conventional units. Coagulation parameters, hemoglobin A1c, direct bilirubin, and indirect bilirubin will not be summarized.

Quantitative clinical chemistry, hematology, and urinalysis results will be summarized by treatment group using descriptive statistics at baseline and at each post-baseline visit. The change and percent change from baseline will also be summarized.

Additional summaries will be provided by scheduled visits for the number and percentage of patients with

- Total CK > 5x ULN
- Hg < 10 mg/dL
- HCT < 30%
- platelets < 100,000 /microL
- WBC < LLN

All clinical safety laboratory data will be presented in by-patient data listings. A separate listing for central laboratory normal ranges, by lab category, lab test, lab parameter, sex, and age, will be presented.

8.3.1. Treatment Emergent Abnormalities

Quantitative laboratory tests will be assigned grades based on National Cancer Institute Common Terminology Criteria for Adverse Events (NCI CTCAE) Version 5. For each applicable laboratory test, a treatment emergent abnormality will be defined as a post-baseline through Week 16 CTCAE grade increase of ≥ 2 grades.

The number and percentage of patients overall and by laboratory test, with any treatment emergent laboratory abnormality, CTCAE increase of ≥ 2 grades, will be presented. Similarly, the number and percentage of patients overall and by laboratory test, with CTCAE increase of ≥ 1 grade will be presented.

CONFIDENTIAL

Estimated glomerular filtration rate (eGFR) is calculated by the central lab using the Chronic Kidney Disease Epidemiology Collaboration (CKD-EPI) equation. eGFR does not have a normal range within the central lab data. A normal range will be defined as \geq 90 mL/min/1.73m2.

LDL cannot be graded via NCI CTCAE version 5. For the purposes of treatment emergent abnormalities, LDL will be graded as follows:

• Optimal: < 100 mg/dL

• Near or Above Optimal: 100 – 129 mg/dL

• Borderline High: 130 – 159 mg/dL

• High: 160 - 189 mg/dL

• Very High: > 189 mg/dL

Listings will be presented for any patient with any treatment emergent laboratory abnormality (post-baseline through Week 16 CTCAE increase of \geq 2 grades). Normal ranges provided by the central laboratory will be presented in a listing.

The number and percentage of patients meeting each criterion detailed in Table 11 will be presented. A listing will be presented for any patient meeting any of the criteria in Table 11.

Final, Version 2.0, 26JULY2023

CONFIDENTIAL

Table 11 Liver Function Tests Potentially Reflecting Hepatoxicity Liver Function Tests

Liver Function Tests	Range of Test Values
ALT or AST	\geq 3 to \leq 5 x ULN
	\geq 5 to < 10 x ULN
	≥ 10 to < 20 x ULN
	≥ 20 x ULN
Total bilirubin	> ULN
	≥ 1.5 x ULN
	\geq 2 × ULN
(AST or ALT) plus total bilirubin	\geq 3 x ULN (ALT or AST) plus \geq 1.5 x ULN
	(total bilirubin)
	\geq 3 x ULN (ALT or AST) plus \geq 2 x ULN (total
	bilirubin)
ALP	\geq 2 x ULN
ALP and total bilirubin	\geq 2 x ULN (ALP) and \geq 2 x ULN (total
	bilirubin)
	$< 2 \times ULN (ALP)$ and $\ge 2 \times ULN (total)$
	bilirubin)
	\geq 2 x ULN (ALP) and \leq 2 x ULN (total
	bilirubin)
ALT = alanine aminotransferase; AST =	aspartate aminotransferase; ULN = upper limit of

ALT = alanine aminotransferase; AST = aspartate aminotransferase; ULN = upper limit of normal; ALP = Alkaline phosphatase.

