8.1.9.1. Blinded Laboratory Assessments

Laboratory results that could potentially unblind the study will not be reported to investigative sites or other blinded personnel until the study has been unblinded unless deemed necessary for patient safety or clinical decision-making during the study. This includes all PD analyses listed in Appendix 2. All clinical safety laboratory assessments listed in Appendix 1 will be available to investigative sites for safety monitoring, except for the analytes noted below.

Analyte and Rationale for Blinding	Details and Risk Mitigation, if Needed
Analyte and Rationale for BlindingFasting lipidsLipid profile changes are an importantPD marker of THR-β agonism.TERN-501 led to significant decreasesin circulating lipid levels includingLDL cholesterol, Apo B, totalcholesterol, and triglycerides in theFIH study (Study TERN501-1009).	Details and Risk Mitigation, if Needed While a standard lipid panel will be included as part of the chemistry panel for eligibility, the lipid parameters collected as TERN-501 PD markers listed in Appendix 2 will be blinded. Declines in lipid parameters including LDL cholesterol, Apo B, total cholesterol, and triglycerides are not expected to pose a safety risk to patients during study participation. However, in the event of LDL cholesterol elevation > 100 mg/dL that is >20% increase from baseline, LDL
Sex hormones THR-β agonism upregulates SHBG expression, and a significant increase in SHBG was demonstrated in the FIH study (Study TERN501-1009). With an increase in SHBG, increases in total testosterone levels were also observed.	cholesterol values will be made available to the Investigators, along with the Medical Monitor and Sponsor, to help guide clinical decision making. Sex hormones including total and free testosterone, estradiol, FSH, and luteinizing hormone (LH) will be blinded. Possible changes in sex hormone levels would need to be interpreted in the context of SHBG levels and are not expected to pose a safety risk to patients during study participation. Sex hormone results may be made available at the Investigator's request upon consultation with Medical Monitor as needed for management of clinical concerns consistent with sex hormone abnormalities.

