9.4.5. Safety Endpoints

In addition to the secondary endpoint of patient incidence of TEAEs, patient incidence of TEAEs will also be summarized by maximum intensity and study drug causality. Summaries of treatment-emergent SAEs will be summarized in the same manner as the secondary endpoint.

Vital signs and quantitative safety laboratory measurements will be summarized by treatment group and scheduled time points. Laboratory abnormalities will be graded according to NCI CTCAE Version 5.0, where applicable. The number and percentage of subjects experiencing treatment-emergent graded lab toxicities will be summarized by treatment group and toxicity grade.

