8.3.5. Shifts in Normal Range

Shift tables for each laboratory test (hematology, chemistry, and urinalysis) showing the shift from normal at baseline to abnormal at each post-baseline visit will be presented by visit. Summaries will present the number and percentage of patients with shifts by treatment group. Denominators for percentages will be the number of patients with non-missing data at the specific assessment and baseline.

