8.5. Electrocardiograms

Summary statistics will be provided for heart rate, PR interval, QRS interval, QT interval, and QTcF at each visit. The investigator interpretation is collected as normal, abnormal not clinically significant (NCS), or abnormal clinically significant (CS). Patients whose interpretation shifts from normal to abnormal (CS or NCS) will be listed separately including description of the abnormality and any associated comments.

Categorical summaries will for baseline, worst post-baseline, and change from baseline for the following QTcF values will be presented:

- > 450 msec
- > 480 msec
- > 500 msec
- Change from baseline > 30 msec
- Change from baseline > 60 msec

CONFIDENTIAL

All ECG results will be presented in by-patient data listings. If applicable, cardiologist consult information will be presented in a separate by-patient data listing.

CONFIDENTIAL

9. Other Assessments

Other assessments will be provided in by-patient data listings only; no summary tables will be provided, including but not limited to the following:

- Eligibility details including unmet eligibility criteria
- Informed consent
- Randomization schema
- Physical examination collection information
- Serology
- Pregnancy testing
- FSH test
- Urine drug screen
- Alcohol test
- Urinalysis and Urine Microscopic Examination
- Coagulation
- Hemoglobin A1c
- Direct bilirubin
- Indirect bilirubin
- Laboratory reference ranges
- Cardiology consult
- Overdose
- Comments

Final, Version 2.0, 26JULY2023

CONFIDENTIAL

10. Changes to Protocol Planned Analyses

There were no changes from the protocol planned analyses.

CONFIDENTIAL

Statistical Analysis Plan CONFIDENTIAL Labcorp Drug Development Study: 000000231152 Protocol Reference: TERNCB-2002

11. Appendices

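### The SAP has no laboratory table by CTCAE grade, although Protocol 9.4.5 plans one, and its two-grade rule leaves worsening from Grade 2 to 3 or Grade 3 to 4 outside the treatment-emergent count and listing

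*SAP*

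**What the plan says.** Protocol Section 9.4.5 has laboratory abnormalities graded by CTCAE Version 5.0 where applicable, and then: "The number and percentage of subjects experiencing treatment-emergent graded lab toxicities will be summarized by treatment group and toxicity grade". It does not define treatment-emergent for laboratory values and does not ask for a listing.

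SAP Section 8.3.1 supplies the definition: "a treatment emergent abnormality will be defined as a post-baseline through Week 16 CTCAE grade increase of ≥ 2 grades". Three outputs follow:

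- the number and percentage of patients meeting that definition, overall and by test;
- a second count, overall and by test, of patients "with CTCAE increase of ≥ 1 grade will be presented";
- a listing tied to the two-grade definition: "Listings will be presented for any patient with any treatment emergent laboratory abnormality".

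The same section assigns LDL to five bands, because CTCAE Version 5 does not grade it, and presents liver tests by multiples of ULN in Table 11 with their own counts and listing. The shift tables in SAP Section 8.3.5 are limited to "showing the shift from normal at baseline to abnormal at each post-baseline visit will be presented by visit". SAP Section 10 states: "There were no changes from the protocol planned analyses".

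**The concern.** The protocol names two dimensions for this table, treatment group and toxicity grade. The SAP keeps the first and drops the second without saying so. A team programming from the SAP would omit a planned safety table, and a reader of Section 10 would have no reason to look for it.

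Grade 3 and 4 are levels that the protocol itself acts on: Section 8.1.9 calls for repeat testing and follow-up when clinically significant laboratory abnormalities shift to those grades. Appendix 6 keeps a laboratory abnormality without signs or symptoms out of adverse event reporting, so the adverse event tables by CTCAE grade will not fill the gap. Some abnormal baselines are to be expected, since Section 5.2 admits patients with ALT or AST up to 5 × ULN, triglycerides up to 500 mg/dL and HbA1c up to 9.5%. A patient who starts abnormal has fewer grades left to climb, so a fixed two-grade step is harder for that patient to meet.

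**Working it through.** No stated power or sample-size figure is involved. The check enumerates the grade moves and then compares the displays.

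**Inputs.** The two-grade definition, the one-grade count and the listing rule from SAP 8.3.1; the by-grade requirement from Protocol 9.4.5. Assumption: the analyte uses the full laboratory scale, Grade 0 to 4, with baseline and post-baseline values graded on the same scale. The documents do not reproduce the CTCAE tables, and some analytes may use fewer grades.

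**Enumeration.** Upward moves from baseline Grade 0, 1, 2 and 3 number 4 + 3 + 2 + 1 = 10.

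| Baseline grade | Rise of at least 2 (treatment-emergent, listed) | Rise of exactly 1 (neither) |
|---|---|---|
| 0 | 0→2, 0→3, 0→4 | 0→1 |
| 1 | 1→3, 1→4 | 1→2 |
| 2 | 2→4 | 2→3 |
| 3 | none | 3→4 |

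Six moves qualify and four do not. Moves ending in Grade 3 are 0→3, 1→3 and 2→3; moves ending in Grade 4 are 0→4, 1→4, 2→4 and 3→4; together 3 + 4 = 7. Five of the seven qualify; 2→3 and 3→4 do not. From Grade 3 the largest possible rise is 4 − 3 = 1, so the definition cannot be met.

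The one-grade count contains all ten moves as a single number per test and arm. It cannot separate 3→4 from 0→1.

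**Other displays.**

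- Table 11 counts and lists ALT/AST, total bilirubin and ALP by ULN multiple, whatever the baseline. It does not use CTCAE grade and does not include GGT.
- SAP 8.3 adds threshold counts for total CK, hemoglobin, hematocrit, platelets and WBC.
- The 8.3.5 shift tables start from normal, so they miss patients already abnormal at baseline.
- Descriptive summaries of change by visit, and by-patient listings of all safety laboratory data, are planned. They hold the values but give no count by grade.

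The analytes left without a by-grade or threshold count therefore include GGT, triglycerides, glucose and electrolytes, so far as CTCAE Version 5 grades them.

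**LDL, a side check.** Bands: below 100, 100–129, 130–159, 160–189, above 189 mg/dL. Protocol 8.1.9.1 releases blinded values "in the event of LDL cholesterol elevation > 100 mg/dL that is >20% increase from baseline".

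| Move (mg/dL) | Rise | Bands moved |
|---|---|---|
| 110→155 | 45/110 = 40.9% | 1 |
| 100→159 | 59/100 = 59.0% | 1 |
| 130→189 | 59/130 = 45.4% | 1 |
| 100→129 | 29/100 = 29.0% | 0 |
| 130→159 | 29/130 = 22.3% | 0 |

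All five meet the release criterion and none is treatment-emergent under a two-band rule. The last two are also outside the one-step count. These are constructed pairs, not expected frequencies.

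**The case against.** The strongest reply is that the SAP presents a good deal of laboratory safety data and that Protocol 9.4 leaves the details to it. Much of this stands, and it limits what a reader should infer.

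- *Patients worsening 2→3 or 3→4 are not counted.* Not so. They are in the one-grade count, and their values are in the general laboratory listings. What is missing is the grade reached and a listing that picks them out.
- *The two-grade threshold contradicts the protocol.* The documents do not support this. Section 9.4.5 leaves treatment-emergent undefined for laboratory values and requires no listing. The threshold is a restrictive choice; the conflict is the absent tabulation by grade.
- *Liver enzyme worsening is hidden.* Largely answered by Table 11. Entry excludes ALT or AST above 5 × ULN, so a later rise above that level enters a higher band and is listed.
- *The LDL bands breach the protocol.* They do not. Grading by CTCAE is required only where applicable, the SAP says LDL cannot be so graded, and the Section 8.1.9.1 criterion governs release of blinded values, not an analysis. LDL change is also analysed by ANCOVA under SAP 7.18.

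The reply does not supply the by-grade table, and it does not make the statement in SAP Section 10 accurate.

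**Conclusion.** The concern holds in a limited form. The SAP omits the toxicity-grade dimension that Protocol 9.4.5 plans, and does not declare the omission. In addition, its definition and abnormality listing leave out 4 of 10 upward grade moves and 2 of the 7 that end in Grade 3 or 4, and exclude patients at Grade 3 at baseline altogether. Those moves are counted only in a pooled figure that hides severity.

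The practical gap is mainly in graded analytes outside Table 11 and the Section 8.3 thresholds. GGT is the clearest example: the protocol reports rises above placebo with TERN-501 10 mg in the first-in-human study, although values stayed below ULN and 10 mg is not a TERN-501 dose in this trial.

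The enumeration rests on a full 0 to 4 scale. The documents give no distribution of baseline grades, so the number of patients affected cannot be estimated. The point concerns safety display; data capture, patient monitoring and the primary endpoint are not affected. It should be corrected because a planned table would otherwise be missing.

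**What to change.** In SAP Section 8.3.1:

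1. Tabulate patients with any post-baseline increase of at least one CTCAE grade by treatment group, test and maximum post-baseline grade. All ten moves are then counted, and all seven that end in Grade 3 or 4 appear under that grade.
2. List every patient who worsens to Grade 3 or 4.
3. Keep the count of rises of at least two grades as a supplement.
4. If any departure from Protocol 9.4.5 remains, declare and justify it in SAP Section 10.

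Optionally, add a descriptive count of patients whose LDL exceeds 100 mg/dL and is more than 20% above baseline, since one-band or within-band rises can meet that criterion without being treatment-emergent under the SAP.

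The cost is SAP wording plus one reformatted table and listing, from values the SAP already plans to grade. The drawback is that more low-grade abnormalities will be displayed.
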